6.4.4 Method of Study Drug Assignment, Randomization and/or Stratification

A centralized randomization computerized program will provide randomized study drug assignment at enrollment through an interactive, web-based electronic data capture (EDC) system (i.e., integrated randomization within the Medidata® platform), using randomization schemes (permuted block method) provided by the sponsor's designee. After a subject qualifies for enrollment in the study, the designated staff at the clinical site will enter confirmation that the subject meets all of the inclusion criteria and none of the exclusion criteria into the system (available 24 hours a day, 7 days a week). Upon successful randomization, the subject will be assigned a unique subject randomization number.

Subjects will be randomized via the interactive web-based system in the order that they qualify, with stratification based on clinical site as well as by the urgency of the cardiac catheterization/PCI procedure at the time the operator decides to perform it- Elective versus Urgent- to obtain balance across treatment groups. Subject randomization numbers that are assigned to subjects who do not receive study drug will not be re-utilized. No enrollment caps will be set for the individual clinical sites or stratum.

6.4.5 Selection and Timing of Dose for Each Subject

All subjects who fulfill study entry criteria as specified in **Sections 6.3.1-6.3.2** and undergo successful randomized treatment assignment will receive PZ-128 or matching placebo, as determined by the randomization scheme: a single, weight-adjusted IV dose of 0.3 mg/kg or 0.5 mg/kg. The infusion must be started within 1 hour before the commencement of the cardiac catheterization procedure (i.e., coronary angiography). [REDACTED]

There is no provision for delaying the start of the study drug administration outside of the pre-diagnostic angiography window.

There is no provision for dose modification (increase or decrease), and this is not allowed. See **Sections 6.4.7.7 and 6.7.2.3**, however for information concerning temporary study drug infusion interruption or permanent discontinuation. The single dose of PZ-128 will be one of two possible dose levels being studied in a parallel manner- 0.3 mg/kg and 0.5 mg/kg- and the dose groups will enroll in parallel until the appropriate number of subjects have been treated.

6.4.6 Blinding of Study Drug

This will be a double-blind study. Study drug treatment assignment (activity of IP) will be blinded for subjects, investigators and staff who evaluate subjects and their responses or make decisions about subject care, and sponsor personnel who are involved in the data analysis. Statisticians and programmers at the sponsor's designated partner (Research Triangle Institute, International- RTI) will prepare all randomization schemes which will then be loaded into the randomization system by Medidata Solutions, Inc. In addition, copies of the randomization schemes will be made available to the following within the sponsor and/or its designee:

- Independent statistician(s) at RTI to support requests by the DSMB
- Study lead(s) for the analysis of the pharmacokinetic and pharmacodynamics samples, exploratory biomarker samples and pharmacogenomics samples.

Appropriate personnel within Clinical Supplies Management, Inc[®] (CSM) will have access to vial sequencing assignment for proper labeling, packaging and shipment of study drug.

Unblinding of the study drug assignment for a subject at a clinical site should occur only in the event of a medical emergency or serious adverse event for which it is necessary to know the study treatment to determine the appropriate medical management for the subject. This circumstance is extraordinary and will likely impact a minor fraction of the enrolled subjects. Unblinding at the study site for any other reason, including selection of subsequent anti-platelet therapies, will be considered a protocol violation. The investigator is strongly encouraged to contact the Medical Director at Tufts Medical Center before unblinding any subject's study drug assignment, but must do so within 1 working day after the event and must document the unblinding and its rationale in the subject's electronic case report form (eCRF). For emergency unblinding, the investigator should be the individual who authorizes the designated investigational pharmacy staff to proceed with unblinding. When the ability to manage the health or welfare of the study subject is dependent upon the requested information, the information may be revealed by the unblinded designated investigational pharmacy staff immediately and independent of the investigator's authorization. However, this delegation of authority must be documented in advance (i.e., pharmacy policy and procedure manual, study-specific delegation of authority log). In case of any accidental unblinding, the procedures noted above should be followed.

The sponsor, Tufts Medical Center, retains the right to unblind the study drug assignment for

SAEs that potentially require expedited reporting to regulatory authorities.

The external, independent DSMB (**Section 9.3.1**) will be allowed to inspect unblinded results for bleeding, platelet aggregation, MACE and stent thrombosis and other SAEs if it is felt necessary to make decisions about enrolling subjects into any dose group. The operating procedures of the DSMB will be defined in a separate charter.

The sponsor and DSMB will monitor all episodes of unblinding.

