One blood sample for DNA, RNA and microRNA analysis will be collected just before the administration of the study drug. Pharmacogenomics analysis will be undertaken to investigate whether DNA polymorphisms, RNA levels and microRNAs correlate with the expression of genes involved in thrombosis, inflammation, and cardiometabolic diseases and whether these genetic components correlate with PZ-128 outcomes. The samples will be analyzed by the sponsor and/or at one of the participating clinical sites under non-GLP conditions.

Subjects at Select Clinical Site(s) Participating in the PK/PD Sub-study

- **Pharmacodynamics- Platelet Aggregation (Whole Blood): Just Prior to Study Drug Infusion, Select Times During Hospitalization, 24-hour/Discharge, 14-day Visit**

Blood samples will be collected just before the administration of the study drug, then 30 minutes \pm 5 min, 1 hour \pm 5 min, 2 hours + 15 min (immediately after completion of infusion), 6 hours – 2 h (4 to 6 h) and 24 hours \pm 2 h or discharge (whichever occurs sooner) after the start of the study drug infusion and at the 14-day visit. After the 24-hour collection, if a subject remains in the hospital for \geq 48 hours, a blood sample will be collected just prior to discharge. The samples will be analyzed using light transmission aggregometry (LTA) on-site under non-GLP conditions.

- **Pharmacokinetics (Plasma): Just Prior to Study Drug Infusion, Select Times During Hospitalization, 24-hour/Discharge, 14-day Visit**

Blood samples will be collected just before the administration of the study drug, then 30 minutes \pm 5 min, 1 hour \pm 5 min, 2 hours + 15 min (immediately after completion of infusion), 6 hours – 2 h (4 to 6 h) and 24 hours \pm 2 h or discharge (whichever occurs sooner) after the start of the study drug infusion and at the 14-day visit. After the 24-hour collection, if a subject remains in the hospital for \geq 48 hours, a blood sample will be collected just prior to discharge. The samples will be analyzed by the sponsor/sponsor's designee under non-GLP conditions.

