7.0 STATISTICAL AND ANALYTICAL PLAN

7.1 Study Design

This is a multi-center, prospective, randomized, double-blind, placebo-controlled, balanced-parallel-groups study to evaluate the safety of PZ-128 compared with placebo, given in addition to standard of care, in subjects undergoing non-emergent PCI or non-emergent cardiac catheterization with the intention to perform PCI.

Prior to coronary angiography, approximately 600 subjects are expected to be randomized in a 2:2:1:1 parallel, double-blind fashion to a single, 2-hour continuous intravenous infusion of either: PZ-128 0.3 mg/kg, PZ-128 0.5 mg/kg, or Placebo 0.3 mg/kg, or Placebo 0.5 mg/kg (the two placebo groups will be merged for the purposes of data analysis). The study drug infusion will be initiated within one hour prior to the start of the cardiac catheterization procedure (i.e., angiography).

The planned administration of GPI for a subject excludes that subject from participation in this study. During PCI, bail-out GPI may be used, at the investigator's discretion, in subjects with new ischemia on telemetry or ECG, worsening of angiographic coronary flow during procedure, or thrombotic complication related to stenting during PCI.

Subjects meeting the inclusion/exclusion criteria (**Section 6.3.1 and Section 6.3.2**) will follow the randomization procedures (**Section 6.4.4 and Section 6.5.2**). The randomization code and starting seed will be generated and maintained by RTI. It will not be provided to the sponsor, or sites until the database has been locked with the exceptions of parties listed in **Section 6.4.6**. The randomization will be generated using random permuted blocks, stratified by clinical site according to the urgency of the procedure at the time the operator decides to perform the cardiac catheterization (i.e., elective versus urgent).

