9.3.6 Central Research Lab- Tufts Center for Hemostasis and Thrombosis Research

Tufts Center for Hemostasis and Thrombosis Research at Tufts Medical Center (study sponsor) will serve as the recipient and processing/distribution center for samples for the following research tests and will perform the analysis on the samples unless otherwise indicated:

- Cardiac Troponin I (sponsor will send samples to a designated laboratory for analysis and provide results to the CEC members for adjudication purposes related to suspected MI cases)
- Exploratory Biomarkers- thrombin in complex with anti-thrombin III: TAT and MMP-1
- Pharmacokinetics (sponsor will send samples to a designated laboratory for analysis)
- Pharmacodynamics (sponsor will perform LTA only for the Tufts Medical Center clinical site)
- Pharmacogenomics- DNA, RNA and microRNA analysis (sponsor may send samples to one of the participating clinical sites to perform analysis)

All of the above-listed tests are being conducted for research purposes only. The subject's individual results will not be returned to the corresponding investigator but will be transmitted electronically to the study's research laboratory database by the sponsor.

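### Leads for PD and biomarker samples may hold the randomisation schemes before lock, and nothing separates them from the staff who run those assays

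*Combined protocol and SAP*

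**What the plan says.** Section 6.4.6 opens with the blinding rule. Besides subjects, it covers "investigators and staff who evaluate subjects and their responses or make decisions about subject care". On the sponsor's side it extends to "sponsor personnel who are involved in the data analysis". It then says that "copies of the randomization schemes will be made available to the following within the sponsor and/or its designee", and names two groups: independent statisticians at RTI who support the DSMB, and "Study lead(s) for the analysis of the pharmacokinetic and pharmacodynamics samples, exploratory biomarker samples and pharmacogenomics samples".

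Section 7.1 says of the randomisation code: "It will not be provided to the sponsor, or sites until the database has been locked with the exceptions of parties listed in" (the reference is to Section 6.4.6). The sample leads are therefore outside the pre-lock embargo.

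On the measurements themselves:

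- Section 6.7.1.4 lists inhibition of platelet aggregation as item 3 of the other secondary efficacy endpoints, at select sites.
- Section 6.6.3.2 says of the PD samples: "The samples will be analyzed using light transmission aggregometry (LTA) on-site under non-GLP conditions". Section 9.3.6 adds that the "sponsor will perform LTA only for the Tufts Medical Center clinical site".
- Sections 6.6.3.2 and 9.3.6 place the biomarker assays with the sponsor. Section 9.3.6 and Appendix E place the genetic analysis there too, with possible help from a participating site.
- PK samples go to a designated laboratory (Section 9.3.6).
- Section 6.3 lists Tufts Medical Center, the sponsor, as one of the three enrolling sites.

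**The concern.** A double-blind comparison of a laboratory endpoint is protected only if the people who produce and process the measurements do not know the arm. Here the people who lead that work are given the allocation, and two of the assay streams (LTA for one site, and the biomarkers) run inside the same institution. If knowledge of the arm reaches whoever runs the assay, decides how a reading is handled or prepares the data, the difference between PZ-128 and placebo can shift without leaving a trace.

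The PD result matters even though it is not primary. Section 4.2.1 says the PK/PD data will be used before the programme moves to Phase 3. Section 6.4.6 lets the DSMB look at unblinded aggregation results when it decides about enrolment into a dose group.

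There is a second, smaller exposure. What is shared is the scheme, not a list of treated subjects. Schemes are prepared in advance as permuted blocks, stratified by site and urgency (Sections 6.4.4, 6.4.6 and 7.1), so a copy may plausibly show assignments not yet made. The sponsor is also an enrolling site.

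**Working it through.** The point contains no figure to recompute. The check is whether the sections, read together, permit what is described and whether any of them closes the gap.

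1. **Who gets the schemes.** Section 6.4.6 names the sample-analysis leads, located within the sponsor or its designee. A given lead could sit with a designee. However, the sponsor's own centre does the biomarker and genetic work and part of the LTA.

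2. **When.** Section 6.4.6 gives no date. The timing follows from Section 7.1, which withholds the code until lock except for the Section 6.4.6 parties. Access before lock is therefore allowed.

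3. **What they lead.** PD is a secondary efficacy endpoint. Biomarkers and pharmacogenomics are exploratory (Section 6.7.1.5). Section 7.9.3 compares biomarker changes between arms and correlates them with outcomes. Appendix E has the sponsor obtain clinical outcomes from RTI and relate them to the genetic results. These activities look like the sponsor data analysis that the blinding rule in Section 6.4.6 is meant to cover.

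4. **Is there a firewall?** Sections 6.4.6, 6.6.3, 7.1, 7.9 and 9.3.6 do not say that LTA readers or assay staff are blinded, or that they are kept apart from the leads. They also give no reason why the PD, biomarker or pharmacogenomics leads need the schemes.

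5. **How access is handled elsewhere.** The site pharmacist obtains an individual subject's assignment through a restricted login (Sections 6.4.1 and 6.4.7.6). The ability to link genetic data to identity is limited to two designated staff (Appendix E). The sample leads are given the scheme with no comparable limit stated.

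6. **Reach by data type.**
   - PD: select sites only. The sponsor reads only its own site's samples, and nothing shows that LTA operators elsewhere hold the scheme.
   - Biomarkers: assayed by the sponsor, from consenting subjects at all sites.
   - Pharmacogenomics: one pre-dose sample, which treatment cannot alter. Any exposure lies in later analysis choices and in custody of the list.
   - PK: assayed by a designated laboratory.

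7. **When release would be safe.** Research results go to a separate research laboratory database (Sections 6.6.3 and 9.3.6), and genetic samples may be analysed up to 15 years after the trial ends (Appendix E). Clinical database lock may therefore come before some assays are complete, so it is not a sufficient release point on its own.

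**The case against.** The strongest reply is that this is a disclosed design choice. Section 6.4.6 states a rule and then its exceptions, and Section 7.1 repeats the exceptions. That is right. A reader might infer that the two sections contradict each other, but they do not once the exception clause is read.

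Second, a reader might infer that the aggregation curves are read unblinded. The documents do not say so. The recipients are leads, and no section says that a lead runs or reads an assay. What is shown is permitted access without a stated barrier.

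Third, a reader might infer that LTA leaves the operator free choices, because Section 7.9.2 gives agonist ranges (SFLLRN 5-20 µM, thrombin 1 nM to 1 µM) and allows an SFLLRN of equal potency. The ranges may simply span a fixed set of tested concentrations. Phase 1 reports SFLLRN at 8, 12 and 20 µM and ADP at 5 and 20 µM (Section 4.1.2.2). Detailed sample procedures are in a Research Laboratory Manual that is not among the documents. The point does not depend on this.

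Fourth, a reader might infer that the primary bleeding comparison is compromised. No section gives the sample leads a role in screening or enrolment, randomisation is central, and only bleeding events adjudicated by the blinded events committee enter the analysis (Sections 7.5 and 9.3.2). Adjudication would not repair a concealment failure at entry. But such a failure would require a lead to pass the list to enrolling staff, and nothing suggests that this would happen.

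Finally, the PD and biomarker results are descriptive (Sections 7.9.2 and 7.9.3). That limits the consequence but does not supply a reason for the access.

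**Conclusion.** The point holds as a permitted and avoidable exposure to bias in the PD and biomarker comparisons. It is more than missing detail, because the plan states an access rule and that rule runs against the purpose of its own blinding sentence. Revision is warranted, but the point does not threaten the primary result.

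The size of any bias cannot be derived from the documents. The extent is limited to LTA where a scheme holder can influence the readings (most plausibly at the Tufts site) and to the biomarker assays run by the sponsor. It does not extend to genotype calls, and it is not shown for LTA at other sites. The allocation list inside an enrolling institution is a theoretical concealment risk only.

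This rests on two assumptions: that at least some of the leads work at the sponsor, and that documents not available here (the laboratory manual, for example) do not already impose a firewall. If they do, the remaining change is to state it in the protocol.

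**What to change.** In Section 6.4.6:

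- Remove the PD, biomarker and pharmacogenomics leads from the recipients of the schemes.
- State that assignments are released to them only after both clinical database lock and finalisation of the corresponding assay results.
- State that LTA readers at every participating site, and biomarker assay staff, are blinded.
- If the PK laboratory must know which samples are placebo, have the independent statistician at RTI, who already holds the schemes, send only the IDs of samples already collected, and never the scheme.

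Align the exception in Section 7.1 with the shortened list.

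The cost is a wording change in two sections, a sample-ID transfer step if PK needs it, and later access for the leads. Assay load does not increase, because placebo PD and biomarker samples must be measured anyway for the between-group summaries. Doses, visits and sample size are unaffected.

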6.4.7 Investigational Product(s)

The investigator shall take responsibility for and shall take all steps to maintain appropriate records and ensure appropriate supply, handling, storage, distribution, and usage of these materials in accordance with the protocol and any applicable laws and regulations. The investigator will designate a qualified (i.e., licensed/registered) member of the institution's research/investigational pharmacy staff to perform the day-to-day pharmacy activities and investigational product management including, but not limited to, the procurement, storage, preparation, dispensing, and final disposition of investigational products, keeping in mind that all aspects of the investigational trial, including conduct, management, and record maintenance, are ultimately the responsibility of the investigator. Neither the investigator nor any member of the clinical research team should have access to the investigational product supply or accountability records in a manner that would jeopardize the maintenance of the blind. See the *Investigational Product Instruction Manual (IPIM)* for complete details and requirements for study drug packaging, labeling, storage, preparation, administration and accountability

6.4.7.1 Identity of Investigational Product(s)

Investigational Products (IP) are active PZ-128 and its matching placebo. The PZ-128 is available as a sterile, preservative-free, white to off-white, solid lyophilized powder cake for reconstitution.

Each PZ-128 or placebo vial is intended for single-dose/single-use only and is not to be used to treat more than 1 subject.

6.4.7.2 Source

PZ-128 and matching placebo will be provided free of charge by the sponsor, Tufts Medical Center, and will be distributed by the sponsor's designee, Clinical Supplies Management, Inc[®]

(CSM, Fargo, ND).

6.4.7.3 Labeling

Information provided on the labels for the IP will comply with ICH, GCP and local regulatory requirements. All vial labels will contain a unique vial sequence number, lot number, study number, product identity (i.e., PZ-128 48 mg/vial or Placebo), vial size (20 cc), reconstitution/ dilution instructions, storage conditions, sponsor identification, IP form (powder for solution for infusion), method of administration (for intravenous use) and investigational statement. All box/carton labels will contain the study number, product identity, number of vials/box, storage conditions and sponsor identification. In lieu of an expiration date, stability information will be provided by the sponsor to the clinical site when the investigational product (IP) is shipped from CSM and will be updated during the clinical investigation.

6.4.7.4 Packaging

Multi-vial boxes/cartons will contain either 20 vials of active PZ-128 or 20 vials of placebo. The sponsor will request the initial IP supply shipment from CSM after the clinical site has completed the appropriate regulatory requirements and prior to the screening of the first subject for study participation. Subsequent IP supply will be requested by each site's designated pharmacy staff according to its ongoing inventory management.

6.4.7.5 Storage

[figure not shown]
Vials of the investigational products must be stored at a controlled freezing temperature of $-20\text{ }^{\circ}\text{C} \pm 10\text{ }^{\circ}\text{C}$ (i.e., $-30\text{ }^{\circ}\text{C}$ to $-10\text{ }^{\circ}\text{C}$ [$-22\text{ }^{\circ}\text{F}$ to $14\text{ }^{\circ}\text{F}$]) and protected from direct sunlight, unless otherwise authorized by the sponsor. The IP supply will be stored in a securely locked location in the site's pharmacy and access should be strictly limited to the designated pharmacy staff.

6.4.7.6 Reconstitution, Dilution and Dispensing

The investigator agrees neither to dispense the study drug from, nor store it at any site(s) other than those listed on the Form FDA 1572. The investigator agrees that study drug(s) will be dispensed by the investigator or subinvestigator(s) named on the Form 1572, or their qualified designee (i.e., prepared for administration and dispensed by registered pharmacy staff). The investigator, subinvestigator(s), or qualified designee(s) also agree that the study drug(s) will be dispensed with a signed medical order from an authorized prescriber only to study subjects who have provided written informed consent, have met all entry criteria and have completed successful randomization (allocation of unique randomization number and assigned study treatment). Investigational product(s) may not be used for any purpose other than that stated in the research protocol.

The designated, unblinded investigational pharmacist at the clinical site will access the

subject's randomized study drug assignment through a password-protected and restricted role login within the Medidata Rave® EDC system prior to the preparation of the blinded IV bag for infusion. The pharmacy staff will select 1 to 2 vials from either the PZ-128 or placebo supply depending upon the subject's assigned IP and dose level (0.3 mg/kg or 0.5 mg/kg) and the subject's actual body weight at the time of Screening (rounded to the nearest kg) in order to provide individual dosing.

[figure not shown]

The final IV bag for administration will be labeled as per the institution's investigational drug policy(s) for blinded products and should include the following: subject name/medical record number/study ID number, blinded IP name (PZ-128/Placebo), IP dosage form (for intravenous infusion), final weight-adjusted dose (mg) and total volume (mL), single-use only, method of administration/infusion rate (IV infusion over 120 min; infuse entire contents for full dose), preparation and expiration dates, storage conditions, study identifier, prescribing investigator name, pharmacist name, and investigational use statement.

